5.5 Outcomes

The nerve conduction along the post-retinal optical pathways will be determined through the evaluation of the RCT through the simultaneous recording of PERG and PEV, the function of the RGCs will be evaluated through the recording of the PERG, the morphological evaluation of the RGCs will be carried out through the OCT evaluations and the morphological and functional evaluation of the nerve structures that form the optical pathways will be performed by means of Cerebral Magnetic Resonance (MRI).

The primary objective is the assessment of changes in the RCT in patients treated with citicoline in oral solution compared to changes in the RCT assessed in patients treated with placebo.

The secondary objectives will be to evaluate whether the changes in RCT in patients treated with Citicoline in oral solution are associated or not with **morphological and functional changes in the nerve structures that form the optical pathways** (NGL, optic tract, visual cortex) and if both conditions may be related to the morpho-functional variations of the RGCs and of the visual field.

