6. ASSIGNMENT AND MASKING

Patients with OAG will be selected from a large cohort of already known diseases and followed at our facility for at least 12 months.

Only patients who meet the inclusion criteria will be selected. Patients will undergo a baseline screening visit during which conditions corresponding to the inclusion criteria will be assessed and the study will be proposed.

Only after the signing of the informed consent, a single investigator ("enrolling physician"), not involved in the clinical and instrumental evaluations, will decide whether to assign the selected patient to one of two groups: treated-Citicoline or treated-Placebo.

The assignment to one or the other group will take place in sequential order of presentation of the patient (with a 1: 1 probability of joining one or the other group) in order to constitute two homogeneous groups in number.

The aforementioned assignment will not be known to the patient and will not be known to the "enrolling physician".

Consequently, during the entire duration of the study (both at the baseline visit and at the 6 and 12 month visit), all evaluations foreseen by the study will be carried out by investigators who will not know whether the patient being examined belongs to the Citicoline-treated group or treated-Placebo.

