9. STATISTICAL ANALYSIS

9.1 Sample size

As already highlighted, the main measure on which we relied for the calculation of the sample size is the RCT.

Our aim is to evaluate the value of the RCT parameter in the group treated with Neurotidine®, compared to that of the group treated with placebo.

We consider the following RCT values: at baseline 70.21 ± 9.12 ms and at the end of treatment 63.3 ± 8.15 ms (19), with an α error of 5% and a power of 80%.

We obtain 27 participants to which we add a drop-out equal to 10%, so the final value is 30 for each group.

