9.2 General methodology

The data of each group, obtained from the PEV, PERG, CV, OCT and RM measurements will be represented by their mean and standard deviation, after having verified their normal distribution by means of the Anderson-Darling and Kolmogorov-Smirnov tests.

For each group, any variations in the measurements indicated above will be evaluated by means of a t-test for paired data.

Furthermore, the parameters of the electrophysiological, morphological and MRI measurements related to the two groups will be compared pre and post treatment, by means of ANOVA with correction of multiple comparisons based on Tukey's method.

The functional electrophysiological parameters (PEV and PERG) will be correlated by Pearson's test with the morphological OCT ones.

Finally, the possible relationship between the PEV, PERG and functional RM parameters of connection of the networks will be assessed using Pearson's test.

This analysis will be repeated respectively between the PEV and PERG parameters and the RM parameters in diffusion for each area indicated in paragraph 5.6.

The p-value of less than 5% is considered significant for any previously exposed test.

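### Sample size in 9.1 allows nothing for multiplicity, but the only between-arm analysis in 9.2 carries Tukey's correction; if that covers the four arm-by-time means, power at 27 per arm is about 57-63%

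*Protocol*

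**What the plan says.** Section 5.5 (Outcomes) defines the primary objective as the "assessment of changes in the RCT in patients treated with citicoline in oral solution compared to changes in the RCT" under placebo. That is a comparison of change with change.

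Section 9.1 (Sample size) rests the calculation on RCT and describes the comparison as one between arms, the comparator being the placebo group: "Our aim is to evaluate the value of the RCT parameter in the group treated with Neurotidine®, compared to that of the group treated with". The planning values are 70.21 ± 9.12 ms at baseline and 63.3 ± 8.15 ms at the end of treatment, "with an α error of 5% and a power of 80" per cent. The result is: "We obtain 27 participants to which we add a drop-out equal to 10%, so the final value is 30 for each group". No test is named and no multiplicity allowance is mentioned.

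Section 9.2 (General methodology) lists paired t-tests within each group, Pearson correlations, and one analysis that compares the arms. In that one, the electrophysiological, morphological and MRI parameters of the two groups "will be compared pre and post treatment, by means of ANOVA with correction of multiple comparisons based on Tukey's method". The threshold for all of these is common: "The p-value of less than 5% is considered significant for any previously exposed test". Section 9.2 does not state which means form the Tukey family, whether the ANOVA is a repeated-measures one, or which contrast decides the primary objective.

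**The concern.** The Tukey-corrected ANOVA is the only analysis in the protocol that compares citicoline with placebo, so as written it is the one available to answer the primary question. Tukey's method raises the critical value for every pair of means in its family. A trial sized for a comparison at an unadjusted 5% does not keep its power if that comparison is then judged at the Tukey threshold. The primary question is a single contrast and needs no such correction.

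Under the four-mean reading, an effect as large as the one planned for would be missed in about 37 to 43 of 100 trials, against about 18 to 22 of 100 for the uncorrected test. A second uncertainty adds to this: the contrast of 5.5 is a difference of changes, and its power depends strongly on whether the ANOVA uses the pairing of each patient's readings.

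**Working it through.** **Inputs.** From 9.1: means 70.21 and 63.3 ms, SDs 9.12 and 8.15 ms, alpha 5%, power 80%, 27 evaluable and 30 enrolled per group. From section 6: assignment "with a 1: 1 probability of joining one or the other group". Assumptions that the protocol does not state: two-sided testing; the before-after change used as the arm difference; the pre-post correlation r where it appears.

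- Difference d = 70.21 − 63.3 = 6.91 ms.
- Pooled SD = √((9.12² + 8.15²)/2) = 8.65 ms.

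**Step 1: the plan's own figure.** A two-sample t-test at two-sided 5% and 80% power needs 26 per arm with SD 8.65 and 29 with SD 9.12 (25 and 28 by the normal approximation). The stated 27 lies within two patients of each. Dropout: 27/0.9 = 30, as stated.

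**Step 2: uncorrected power.** Noncentrality = d/(SD·√(2/n)). At n = 27 this is 6.91/2.354 = 2.94 (SD 8.65) or 6.91/2.482 = 2.78 (SD 9.12). The critical value is t(0.975; 52) = 2.007.

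**Step 3: Tukey over four means (two arms, pre and post).** The critical value is q(0.95; 4, 4(n−1))/√2. At n = 27 this is 3.693/1.414 = 2.611, a per-pair two-sided level of about 1.0%. Power follows from the noncentral t with the same noncentrality, for citicoline-post versus placebo-post.

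| n per arm | SD (ms) | Uncorrected | Tukey, 4 means |
|---|---|---|---|
| 27 | 9.12 | 78.0% | 57.0% |
| 27 | 8.65 | 82.1% | 62.8% |
| 30 | 9.12 | 82.3% | 62.9% |
| 30 | 8.65 | 86.1% | 68.7% |

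Under this rule, 80% power needs 38 (SD 8.65) to 42 (SD 9.12) evaluable per arm.

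**Step 4: sensitivity to the family.** With two means (arms compared separately at each visit), Tukey's critical value equals that of the t-test, 2.007 at n = 27, and nothing is lost. With six means (T2 included) it is 2.885, and power at 27 per arm is 46% (SD 9.12) to 52% (SD 8.65).

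**Step 5: the contrast of 5.5.** The difference in changes has true standard error SD_change·√(2/n), where SD_change = √(9.12² + 8.15² − 2r·9.12·8.15). An ANOVA that treated the four cells as independent would instead use 2·8.65/√27 = 3.33 ms. All results are at n = 27, unadjusted 5%.

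| Assumed r | SD_change (ms) | True SE (ms) | Power, within-patient error | Power, pairing ignored |
|---|---|---|---|---|
| 0.3 | 10.25 | 2.79 | 68% | 54% |
| 0.5 | 8.68 | 2.36 | 82% | 55% |
| 0.7 | 6.75 | 1.84 | 96% | 57% |

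With pairing ignored, the true type I error would be about 0.5% at r = 0.5 and 0.03% at r = 0.7. The loss in the last column comes from the oversized error term; no Tukey correction is applied there.

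**The case against.** The strongest reply is that the protocol never fixes the four-mean family. Comparing the arms before treatment and again after treatment is also a literal reading of 9.2, and then Tukey has no effect. This stands: a reader might infer that the trial simply has 57-63% power, and the text does not support that without the condition. On the two-mean reading, however, the Tukey clause does nothing.

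Second, Tukey governs pairwise comparisons of means. The change-versus-change question of 5.5 is the group-by-time term, which has its own test at 5%. This also stands. The 57-63% belongs to the post-treatment comparison, not to the contrast of 5.5. But 9.2 does not say that the group-by-time term decides the trial.

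Third, a reader might infer that the ANOVA ignores pairing. Section 9.2 says only ANOVA. The same section uses paired t-tests within groups, and the error term may be set out in an SAP that is not shown. The 54-57% is therefore one possible outcome and not a stated defect.

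Fourth, a reader might infer that 9.1 was certainly a two-sample calculation. No test is named, and a paired t-test on the quoted SDs with zero correlation gives exactly 27. The two-arm reading rests on the stated aim and on the number being given for each group.

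Finally, SD 8.15 gives 69% at 27 per arm, but the uncorrected power is then 86%, so that figure should not be read as a fall from 80%.

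**Conclusion.** The mismatch is real, but its size is conditional. Section 9.1 makes no allowance for multiplicity, and the only between-arm analysis in 9.2 carries a correction. Under the smallest family that gives the correction any effect, power for the post-treatment comparison is about 57-63% at 27 per arm (against 78-82% uncorrected) and 63-69% if all 30 per arm complete (against 82-86%). These figures assume a 6.91 ms arm difference, SDs of 8.65 to 9.12 ms and two-sided testing. If the arms are compared separately at each visit, there is no loss.

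For the contrast that 5.5 describes, power turns on the error term and on a pre-post correlation the protocol does not give: 68% to 96% with a within-patient analysis at r of 0.3 to 0.7, and about 54-57% if pairing is ignored. The two sections should be reconciled, since the stated 80% cannot be tied to any identified primary test.

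**What to change.** In 9.2, state that the primary objective is tested by one contrast, the arm difference in RCT change from T1 to T3, with a within-patient error term (change score or repeated-measures group-by-time term), at two-sided 5% and without Tukey's correction. Keep Tukey for the remaining pairwise comparisons.

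If the sponsor does want Tukey to apply to the primary comparison, 9.2 should state the family and 9.1 should restate the power for that family: about 57-63% at 27 per arm for four means.

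The cost is two sentences in 9.2, or a stated family in 9.2 plus one restated figure in 9.1. Neither needs more patients, visits or measurements.

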2. OBJECTIVES AND AIMS OF THE STUDY

- 1) Primary Objective: to evaluate whether treatment with **Citicoline in oral solution** can produce an improvement of the post-retinal nerve conduction, altered base in patients with OAG.
- 2) Secondary objective: to evaluate in patients with OAG whether the possible changes in post-retinal nerve conduction induced by treatment with Citicoline in oral solution (information obtained through electrophysiological recordings) are associated or not with **morphological and functional variations of the nervous structures that form the optical pathways** (NGL, optic tract, visual cortex, information obtained through the acquisition of structural and functional magnetic resonance imaging) and whether both conditions can be related to the morpho-functional variations of the RGCs and of the visual field (CV).

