4. STUDY POPULATION

Sixty patients affected by bilateral OAG, between the ages of 20 and 70, will be enrolled in the study within a maximum time frame of 12 months (see point 9.1 "sample size").

4.1 Inclusion criteria:

- Age between 20 and 70 years old
- Diagnosis of glaucoma. Glaucoma is defined as: glaucomatous damage of the CV (Humphrey 24-2 standard SITA with mean deviation between -6 and -25 dB) and glaucomatous appearance of the optic nerve
- Visual acuity not less than 5/10

- Eye pressure below 21 mmHg with the use of ocular hypotonizing drugs including sympathomimetics, beta-blockers, prostaglandins, beta-adrenergics, carbonic anhydrase inhibitors. Such drugs can be used both alone and in combination with each other.
- Documented post-retinal nerve conduction delay through simultaneous recording of VEP and PERG showing an increase in RCT

4.2 Exclusion criteria:

- Ocular surgery in the 3 months preceding the study, including surgery for cataracts in the previous three months.
- Cataract or maculopathy
- Argon laser trabeculoplasty (ALT) within the previous 6 months
- Known hypersensitivity to the study product
- Secondary causes of ocular hypertension, including systemic or topical use of steroids
- Positive history of ocular or systemic diseases that could preclude enrollment in the study in the opinion of the investigators
- Changes in systemic therapies that could compromise intraocular pressure values (beta-blockers, alpha and beta adrenergics, calcium inhibitors, ACE inhibitors) in the 30 days prior to enrollment
- Ongoing therapy with vasoactive cerebral drugs, neurotrophic, lutein, zeaxanthin, retinal, acid, docosahexaenoic, Ubiquinone and / or its derivatives, Citicoline and / or its derivatives (possible previous treatment with Ubiquinone, L-Carnitine, Citicoline and / or its derivatives must have been suspended at least 6 months prior to inclusion in the study)
- Pregnancy, breastfeeding
- Diabetes
- Systemic lupus erythematosus, rheumatoid arthritis, connectivitis
- Concomitant use of anticoagulants and lithium

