5.5.2. Electrophysiological Evaluations

a) Pattern electroretinogram (PERG)

The PERG shows the bioelectric activity of the innermost layers of the retina (ganglion cells, their fibres). PERG response is characterised by a series of waves with three successive peaks, with polarity negative, positive and negative respectively. In normal people, these peaks have the following implicit times: 35, 50 and 95 msec (N35, P50 and N95). An increase in the N35, P50 and N95 times and a decrease in amplitude N35-P50 and P50-N95 was found in glaucoma patients. These abnormalities in PERG are significantly related to visual field defects and to a reduction in the thickness of the layer of nerve fibres.

Also, PERG has shown a high clinical capacity (sensitivity: 100%, specificity: 100%) to detect malfunctions of the ganglion cells in glaucoma patients (43).

b) Visual evoked potentials (PEV)

VEPs reflect the bioelectric activity of the visual cortex in response to visual stimulation and thus evaluate the function of the visual pathway as a whole. VEP response is characterised by a series of waves with three successive peaks, with polarity negative, positive and negative respectively. In normal people, these peaks have the following times: 75, 100 and 145 msec (N75, P100 and N145). An increase in the N75, P100 and N145 times and a decrease in amplitude N75- P100 and P100-N145 was found in glaucoma patients. These VEP abnormalities are significantly correlated with visual field defects. Also, VEP has shown a high clinical capacity (sensitivity: 100%, specificity: 100%) to detect a delay in the neural conduction along the visual pathways in patients with glaucoma (43).

Comparing VEP and PERG times allows for the obtaining a neural conduction index in the postretinal visual pathways. In fact, the difference between the VEP P100 and P50 times is known as "Retino-cortical Time (RCT)".

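### The Pearson tests in 9.2 are stated on measured parameters, with no change score, visit or arm, while the secondary objective asks whether changes under citicoline go together

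*Protocol*

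**What the plan says.** **Objective.** Protocol section 2 asks "whether the possible changes in post-retinal nerve conduction induced by treatment with Citicoline in oral solution" are associated with structural and functional variations of the optic pathways, and whether both relate to variations of the retinal ganglion cells and the visual field. Section 5.5 repeats it: the aim is to "evaluate whether the changes in RCT in patients treated with Citicoline in oral solution are associated or not" with changes in those structures. Section 10.1 frames the expected result the same way.

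**Analysis.** Section 9.2 states three sets of Pearson tests:

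- Electrophysiology with OCT: "The functional electrophysiological parameters (PEV and PERG) will be correlated by Pearson's test with the morphological OCT ones".
- Electrophysiology with functional MRI: "the possible relationship between the PEV, PERG and functional RM parameters of connection of the networks will be assessed using Pearson's test".
- Electrophysiology with diffusion MRI: "This analysis will be repeated respectively between the PEV and PERG parameters and the RM parameters in diffusion".

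Each is judged at 5%. None mentions change from baseline, a visit or a treatment group. None involves the visual field.

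**The concern.** A correlation between two measurements across patients and a correlation between two changes within patients answer different questions. The first can be strong simply because patients with advanced disease do worse on every test. It would then be just as strong in the placebo group, and would say nothing about whether a patient whose conduction improved also showed a structural or functional change.

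The protocol supplies both ingredients for this in the PERG–OCT pair. Entry spans a wide range of severity, "mean deviation between -6 and -25 dB" (section 4.1), and section 5.5.2 says of this disease: "These abnormalities in PERG are significantly related to visual field defects and to a reduction in the thickness of the layer of nerve fibres". At stake is whether a significant Pearson result is reported as an answer to the secondary objective when it only describes the disease.

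**Working it through.** **1. What 9.2 means by a parameter.** Section 9.2 speaks of variations in the sentence on within-group paired t-tests. It speaks of parameters for quantities compared before and after treatment, that is, quantities that exist at each visit. Section 5.6 lists the efficacy parameters as measured quantities: a latency difference, thicknesses, fractional anisotropy and diffusivities, connectivity Z-scores. The Pearson sentences use parameters. The natural reading is therefore measured values, not change scores.

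**2. Side by side.**

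| | Objective (2, 5.5) | Pearson tests (9.2) |
|---|---|---|
| Quantity | Change in RCT against changes in pathways, ganglion cells, field | PEV/PERG parameters against OCT and MRI parameters |
| Time | During treatment | Not stated |
| Group | Patients on citicoline | Not stated |
| Visual field | Included | Not in any correlation |

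**3. Where a severity-driven correlation is documented.** Section 5.5.2 states it for PERG with visual field and nerve fibre thickness, and for VEP with visual field. For post-retinal conduction against lateral geniculate nucleus, optic tract and cortex, section 1.1 says the relation is not known.

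**4. How much it could matter.** The protocol gives no correlation between measures and no SD of change, so every input here is an assumption except the sample size: 27 per group before drop-out (section 9.1), hence 2 × 27 = 54 for both groups pooled.

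Model: two measures with cross-sectional SD 1 correlate r at baseline. Each then changes independently of the other and of baseline, with SD 0.5 for one and 0.3 for the other. There is no association between the changes.

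The correlation of post-treatment values is

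r / √[(1 + 0.5²)(1 + 0.3²)] = r / √(1.25 × 1.09) = r / 1.167.

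For r = 0.5 this is 0.428. Fisher's z is atanh(0.428) = 0.458. At n = 27, 0.458 × √24 = 2.24, and the chance of exceeding 1.96 is about 61%. At n = 54, 0.458 × √51 = 3.27, giving about 90%. Simulation of 20,000 trials per setting agrees to within about 2 percentage points:

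| Assumed r at baseline | Values, n = 27 | Values, n = 54 | Changes, either n |
|---|---|---|---|
| 0 | 5% | 5% | about 5% |
| 0.1 | 7% | 9% | about 5% |
| 0.2 | 14% | 24% | about 5% |
| 0.3 | 25% | 47% | about 5% |
| 0.5 | 62% | 91% | about 5% |

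Entries are the share of trials with Pearson p<0.05 although the changes are unrelated.

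**5. Sensitivity to the model.** A second model fixes the correlation of values at r at every visit and sets each measure's visit-to-visit correlation at 0.8. Correlating follow-up values then gives 33% and 61% at r = 0.3, and 79% and 98% at r = 0.5 (n = 27 and 54). Correlating changes again gives about 5%. The size depends on the assumptions. The direction does not, as long as r is above zero.

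**The case against.** **The wording is loose, not wrong.** Section 9.2 never says values, and visit, derived variable and arm are details that an analysis plan often settles. This stands in part: that values are meant is an inference, and it lowers confidence. But the protocol does fix the test, the quantities and the threshold, and as worded they do not match its own objective. An analysis of values would satisfy 9.2 without addressing the objective.

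**Severity does not demonstrably drive every pair.** A reader might infer that all the planned correlations are bound to be significant whatever the treatment does. The documents do not support that. The relation is stated for PERG with fibre thickness and field and for VEP with field, but section 1.1 leaves it open for post-retinal conduction with brain structure. For the MRI pairs, r near zero cannot be excluded, and the false-positive rate would then be near 5%. Since that relation is an open question, correlating values also has a legitimate descriptive use.

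**RCT is not named in the Pearson tests.** This is tempting to count as a further defect, but it carries little weight. Section 9.2 names RCT nowhere, even for the primary comparison, and RCT is by definition the VEP P100 time minus the PERG P50 time (sections 5.5.2 and 5.6).

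**Other analyses would show an absence of change.** The paired t-tests and the ANOVA would reveal it if mean structure did not move, so a correlation would not be reported in isolation. That is fair, but neither tests whether changes go together within patients.

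**Conclusion.** The point holds as a mismatch between a stated analysis and the objective it serves. Read as written, the Pearson tests in 9.2 do not measure whether changes move together, and this is true even where values are uncorrelated across patients. For PERG with OCT, a significant result can arise from severity alone and equally on placebo. For the MRI pairs that is possible but not documented.

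The false-positive rates for an association of changes run from about 5% at r = 0 to 62% (n = 27) or 91% (n = 54) at r = 0.5. They rest wholly on assumed correlations and change SDs and should be read as a range, not a prediction. The issue concerns the secondary objective only; the primary RCT comparison is unaffected. It should be corrected. Confidence is moderate, because the reading of parameters as values is inferred from usage in 9.2 and 5.6.

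**What to change.** In section 9.2, state that the correlations for the secondary objective use T1-to-T3 changes: the change in RCT against the change in each OCT, MRI and visual field measure listed in 5.6. Compute them within the citicoline arm with the placebo-arm value beside them, or as partial correlations adjusted for arm. Do not pool the arms unadjusted, because a treatment shift in both measures would create a correlation by itself. Label any correlation of values as descriptive of the disease.

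The cost is wording only: PERG, PEV, OCT, visual field and MRI are all scheduled at T1 and T3 (section 5.2). The downside is that correlations of changes are noisier and likely smaller, so fewer will reach significance with about 27 patients per arm.

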5.6 Efficacy parameters

- 1) For the evaluation of the RCT, the difference of the latency time P100 of the PEV and the latency time P50 of the PERG will be considered.
- 2) For the assessment of the visual field (HFA 24-2 and 10-2), the following will be considered: MS, MD and PSD.
- 3) The following parameters will be recorded for each SD-OCT imaging session:
 - the average thickness of the layer of the peripapillary retinal nerve fibers and the thickness divided by sectors.
 - the average thickness of the neural rim and the thickness divided by sectors
 - the average thickness of the ganglion cell layer and the internal plexiform layer (GCL / IPL) and the thickness divided by sectors
- 4) For each diffusion-weighted MRI acquisition, the following parameters of the thalami and LGN and of the optical tracts will be acquired: fractional anisotropy (FA), average diffusivity (MD, axial (AD) and radial (RD)).
For each acquisition of morphometry based on the voxel, the neuronal density of all cortical areas of the entire brain will be acquired.
For functional MRI at rest, the connectivity strength (Z-score) of all the independent cortical networks (linked to vision and not, independently) will be analyzed, as well as the degree of functional

connectivity between the thalami and the LGN and RSNs detected in the previous independent analysis.

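### Section 9.2 judges every Pearson correlation behind the secondary objective at an unadjusted 5%, so chance structure-function links may be called significant

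*Protocol*

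**What the plan says.** Section 9.2 lists the analyses in order: paired t-tests within each group, a between-group comparison, and three sets of correlations.

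- The between-group comparison is made "by means of ANOVA with correction of multiple comparisons based on" Tukey's method. No other correction appears in the section.
- First correlation set: "The functional electrophysiological parameters (PEV and PERG) will be correlated by" Pearson's test with the OCT parameters.
- Second set: PEV and PERG parameters with the resting-state network measures, also by Pearson's test.
- Third set: "This analysis will be repeated respectively between the PEV and PERG parameters and the RM parameters in diffusion for each area indicated in paragraph 5.6".

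Section 9.2 then ends: "The p-value of less than 5% is considered significant for any previously exposed test".

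Section 5.6 names the candidate measures. For electrophysiology, "the difference of the latency time P100 of the PEV and the latency time P50 of the PERG will be considered", which defines RCT. For OCT there are three average thicknesses (nerve-fibre layer, neural rim, GCL/IPL), each also by sector. For diffusion, "the following parameters of the thalami and LGN and of the optical tracts will be acquired": fractional anisotropy and mean, axial and radial diffusivity. For resting-state imaging, "the connectivity strength (Z-score) of all the independent cortical networks" is analysed, together with the connectivity of the thalami and LGN with those networks.

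Section 5.5 states the secondary objective: "to evaluate whether the changes in RCT in patients treated with Citicoline in oral solution are associated or not with" changes in the structures of the optic pathway, and whether both relate to the ganglion cells and the visual field. Sections 2 and 10.1 say the same in substance.

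**The concern.** The closing sentence of 9.2 reaches back over everything before it, including the three correlation sets. Tukey's method adjusts comparisons of means and does not carry over to correlation coefficients. Read as written, each correlation is therefore declared significant or not at 5% on its own, however many are run.

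This matters because the correlations are the only analysis in 9.2 that addresses association, which is what the secondary objective asks about. The protocol does not call them exploratory or single out key pairs. About 1 in 20 correlations with no true link would be labelled significant, and such a label could be taken as the answer to the secondary objective.

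**Working it through.** **Inputs.** The level is 0.05 per test (9.2). Section 5.6 gives 3 OCT averages and 4 diffusion metrics in 3 structures (thalami, LGN, optic tracts). The sample is 27 per group before drop-out (9.1), so 27 in one arm or 54 pooled. The protocol gives no error rate for the correlations, so there is no such figure to reproduce. The 27 itself is consistent with 9.1: a two-sided 5% comparison of two means at 80% power with a difference of 70.21 − 63.3 = 6.91 ms needs 25 per group with the pooled SD of 8.65, and 28 with the baseline SD of 9.12. Then 27 / 0.9 = 30.

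**Assumptions not in the protocol.** OCT sectors, left/right splits, amplitudes and other peaks are left out. Networks are counted as none, or as one with 3 measures (its own strength, its link to the thalami, its link to the LGN). Anything more raises the counts.

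**Number of tests.**
- P100 and P50 latencies: 2 × (3 + 4 × 3) = 30; with one network, 2 × (15 + 3) = 36.
- RCT alone, if used: 1 × 15 = 15; with one network, 18.

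**Expected false positives if every link is null:** 0.05 × m.
- 30 and 36 tests: 1.5 and 1.8.
- 15 and 18 tests: 0.75 and 0.9.

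These do not depend on how the measures correlate with each other.

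**Chance of at least one, independent measures:** 1 − 0.95^m = 0.537 (15), 0.603 (18), 0.785 (30), 0.842 (36).

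**Chance of at least one, correlated measures.** Simulation with 6,000 runs, all nulls true, n = 54, and an equal correlation among the electrophysiology parameters and within each modality:

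| Tests | 0 | 0.5 | 0.9 |
|---|---|---|---|
| 15 | 0.53 | 0.40 | 0.21 |
| 18 | 0.61 | 0.48 | 0.28 |
| 30 | 0.78 | 0.63 | 0.28 |
| 36 | 0.84 | 0.70 | 0.37 |

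With n = 27 the results are nearly the same. Repeat simulations agree to within about 0.03; one puts the lowest cell at 0.20. The range is therefore about 28% to 84% for the two latencies and about 20% to 60% for RCT alone.

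**If the OCT links are real.** Section 5.5.2 reports that PERG abnormalities relate to nerve-fibre thickness. Dropping all OCT pairs and all networks leaves the diffusion tests only. For the two latencies that is 24 tests, with 24 × 0.05 = 1.2 expected and 1 − 0.95^24 = 0.71 if independent. For RCT alone it is 12 tests, with 0.6 expected and 0.46. The figures fall but stay well above 5%.

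**Under Benjamini-Hochberg at 5% within each modality.** With all nulls true, each modality carries at most about 5%. Two independent modalities give 1 − 0.95² = 0.10, and three give 1 − 0.95³ = 0.14. Simulation over the same cases gives about 0.05 to 0.15.

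**Price in power.** Correlation detectable at 80% power (Fisher z): r = tanh((z + 0.842) / √(n − 3)). The strictest Benjamini-Hochberg step among 12 diffusion tests is 0.05 / 12 = 0.0042, where z = 2.865 in place of 1.960.
- n = 54: from tanh(2.802 / √51) = 0.37 to tanh(3.707 / √51) = 0.48.
- n = 27: from tanh(2.802 / √24) = 0.52 to tanh(3.707 / √24) = 0.64.

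**The case against.** The strongest reply is that these are open-ended secondary analyses in a 60-patient study. Section 10.1 expects that associations may or may not be found, and no correlation supports an efficacy claim. Many statisticians would not adjust such analyses. That is fair, and it is why an exploratory label is an acceptable remedy. It does not rescue the present text, which neither adjusts the correlations nor calls them exploratory, and gives each one a significance verdict.

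A second reply is that the number of tests, the list of parameters and the pooling of arms belong in a statistical analysis plan, which may exist. This stands. Their absence is not a fault here, and the counts above are assumptions. Section 9.2 names PEV and PERG parameters in the correlations and not RCT, so the 15 to 18 range applies only if RCT is used. What does not depend on an unseen document is the stated 5% rule; a later plan that adjusted the correlations would have to depart from it.

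Third, the correlation of 0.9 is assumed. It is plausible among metrics from one diffusion tensor, but less so across brain structures, across OCT layers, or between P100 and P50. It serves as a cautious lower end.

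A reader might infer more than the protocol supports:
- That the efficacy result is at risk. It is not: the between-arm RCT comparison does not depend on the correlations.
- That a false link is almost certain. The chance ranges widely and falls where links are real.
- That a chance link could never be recognised. If all coefficients, p-values and the number of tests are reported, a reader can apply a correction.
- That the trial needs a new confirmatory hierarchy. This defect does not require one.

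**Conclusion.** The point holds for the Pearson correlations. The rule in 9.2 is stated text and, if followed, gives each of them a significance verdict without multiplicity control. On the counts assumed from 5.6 and with all links null, one to two false positives are expected for the two latencies, and just under one for RCT alone. Even at an assumed correlation of 0.9 among the measures, the chance of at least one is about four times the nominal 5% or more. The conclusion rests on those counts, on the all-null premise (doubtful for PERG with nerve-fibre thickness) and on the assumed range of correlation. It concerns the interpretation of the secondary objective only. It is worth correcting because the correction is cheap, but it does not threaten the primary comparison or the sample size.

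**What to change.** Amend the last sentence of 9.2 so that the unadjusted 5% does not apply to the Pearson correlations, and choose one of two treatments:

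- **(a) Adjust.** Apply Benjamini-Hochberg at 5% within each modality (OCT, diffusion, network) to a list of correlations fixed before unmasking.
- **(b) Relabel.** Report the correlations as exploratory, with estimates and confidence intervals, and do not call them significant.

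Either needs a short change of text and no new data or visits. Option (a) costs power: at its strictest step among 12 diffusion tests, the detectable correlation rises from about 0.37 to 0.48 with 54 pooled, or from about 0.52 to 0.64 with 27 in one arm. Because control is per modality, a chance of about 5% to 15% of at least one false link overall remains if all nulls are true. Option (b) costs no power, but no link can then be claimed as significant.
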